## 5.7 Diet/Activity/Other Considerations

### 5.7.1 Diet

Subjects should maintain a normal diet unless modifications are required to manage an AE such as diarrhea, nausea or vomiting.

### 5.7.2 Contraception

Pembrolizumab may have adverse effects on a fetus *in utero*. Furthermore, it is not known if pembrolizumab has transient adverse effects on the composition of sperm. Non-pregnant, non-breast-feeding women may be enrolled if they are willing to use 2 methods of birth control or are considered highly unlikely to conceive. Highly unlikely to conceive is defined as 1) surgically sterilized, or 2) postmenopausal (a woman who is ≥45 years of age and has not had menses for greater than 1 year will be considered postmenopausal), or 3) not heterosexually

9458- Protocol Version Date 28 Feb 2019

active for the duration of the study. The two birth control methods can be either two barrier methods or a barrier method plus a hormonal method to prevent pregnancy. Female subjects should start using birth control from study Visit 1 throughout the study period up to 120 days after the last dose of study therapy.

The following are considered adequate barrier methods of contraception: diaphragm, condom (by the partner), copper intrauterine device, sponge, or spermicide. Appropriate hormonal contraceptives will include any registered and marketed contraceptive agent that contains an estrogen and/or a progestational agent (including oral, subcutaneous, intrauterine, or intramuscular agents).

Men may be enrolled if they are willing to use a condom or are considered highly unlikely to conceive. Highly unlikely to conceive is defined as 1) surgically sterilized, 2) previously known to have azoospermia, or 3) not heterosexually active for the duration of the study. Male subjects should start using condoms from study Visit 1 throughout the study period up to 120 days after the last dose of study therapy.

Subjects should be informed that taking the study medication may involve unknown risks to the fetus (unborn baby) if pregnancy were to occur during the study. In order to participate in the study they must adhere to the contraception requirement (described above) for the duration of the study and during the follow-up period defined in section 7.2.2-Reporting of Pregnancy and Lactation to the Sponsor-Investigator and to Merck. If there is any question that a subject will not reliably comply with the requirements for contraception, that subject should not be entered into the study.

### **5.7.3 Use in Pregnancy**

If a subject inadvertently becomes pregnant while on treatment with pembrolizumab, the subject will immediately be removed from the study. The site will contact the subject at least monthly and document the subject's status until the pregnancy has been completed or terminated. The outcome of the pregnancy will be reported to the PI and to Merck without delay and within 24 hours to the PI and within 2 working days to Merck if the outcome is a serious adverse experience (e.g., death, abortion, congenital anomaly, or other disabling or life-threatening complication to the mother or newborn).

The study investigator will make every effort to obtain permission to follow the outcome of the pregnancy and report the condition of the fetus or newborn to the Sponsor-Investigator and Merck. If a male subject impregnates his female partner the study personnel at the site must be informed immediately and the pregnancy reported to the PI and to Merck and followed as described above and in Section 7.2.2.

### **5.7.4 Use in Nursing Women**

It is unknown whether pembrolizumab is excreted in human milk. Since many drugs are excreted in human milk, and because of the potential for serious adverse reactions in the nursing infant, subjects who are breast-feeding are not eligible for enrollment.

9458- Protocol Version Date 28 Feb 2019

## 5.8 Subject Withdrawal/Discontinuation Criteria

Subjects may withdraw consent at any time for any reason or be dropped from the trial at the discretion of the investigator should any untoward effect occur. In addition, a subject may be withdrawn by the treating investigator or the PI if enrollment into the trial is inappropriate, the trial plan is violated, or for administrative and/or other safety reasons. Specific details regarding discontinuation or withdrawal are provided in Section 7.1.4 – Other Procedures.

A subject must be discontinued from the trial for any of the following reasons:

- The subject or legal representative (such as a parent or legal guardian) withdraws consent.
- Confirmed morphologic relapse/progression
- Radiologic studies highly suspicious for extramedullary relapse (biopsy confirmation is strongly recommended unless prohibitively risky or patient refuses)
- Unacceptable adverse experiences as described in Section 5.2.1.2
- Intercurrent illness that prevents further administration of treatment
- Treating investigator feels that alternative treatment (e.g., allogeneic HCT) would be more beneficial for the subject
- Investigator's decision to withdraw the subject
- The subject has a confirmed positive serum pregnancy test
- Noncompliance with trial treatment or procedure requirements
- The subject is lost to follow-up
- Completed 24 months of uninterrupted treatment with pembrolizumab or 35 administrations of study medication, whichever is later.

*Note: 24 months of study medication is calculated from the date of first dose. Subjects who stop pembrolizumab after 24 months may be eligible for up to one year of additional study treatment if they progress after stopping study treatment provided they meet the requirements detailed in Section 7.1.5.5*

- Administrative reasons

The End of Treatment and Follow-up visit procedures are listed in Section 6 (Protocol Flow Chart) and Section 7.1.5 (Visit Requirements). After the end of treatment, each subject will be followed for 30 days for adverse event monitoring (serious adverse events will be collected for 90 days after the end of treatment as described in Section 7.2.3.1). Subjects who discontinue for reasons other than progressive disease will have post-treatment follow-up for

9458- Protocol Version Date 28 Feb 2019

disease status until disease progression, initiating a non-study cancer treatment, withdrawing consent or becoming lost to follow-up. After documented disease progression each subject will be followed by medical record review and/or telephone for overall survival until death, withdrawal of consent, or the end of the study, whichever occurs first.

### **5.8.1 Discontinuation of Study Therapy after Complete MRD Response**

Discontinuation of treatment may be considered for subjects who have attained a confirmed complete MRD response that have been treated for at least 24 weeks with pembrolizumab and had at least two treatments with pembrolizumab beyond the date when the initial complete MRD response was declared. Subjects who then experience disease progression may be eligible for up to one year of additional treatment with pembrolizumab via the Second Course Phase at the discretion of the investigator if no cancer treatment was administered since the last dose of pembrolizumab, the subject meets the safety parameters listed in the Inclusion/Exclusion criteria, and the trial is open. Subjects will resume therapy at the same dose and schedule at the time of initial discontinuation. Additional details are provided in Section 7.1.5.5.

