#### **7.1.4 Other Procedures**

##### **7.1.4.1 Withdrawal/Discontinuation**

When a subject discontinues/withdraws prior to trial completion, all applicable activities scheduled for the final trial visit should be performed at the time of discontinuation. Any adverse events which are present at the time of discontinuation/withdrawal should be followed in accordance with the safety requirements outlined in Section 7.2 - Assessing and Recording Adverse Events. Subjects who a) attain a CR or b) complete 24 months of treatment with pembrolizumab may discontinue treatment with the option of restarting treatment if they meet the criteria specified in Section 7.1.5.5. After discontinuing treatment following assessment of CR, these subjects should proceed to the Follow-Up Period of the study (described in Section 7.1.5.4).

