#### **7.1.5.3.3 Survival Follow-up**

Once a subject experiences confirmed disease progression or starts a new anti-cancer therapy, the subject moves into the survival follow-up phase and should be contacted (via medical record review and/or telephone) approximately every 3 months to assess for survival status until death, withdrawal of consent, or the end of the study, whichever occurs first.

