### **7.1.5.4 Second Course Phase (Retreatment Period)**

Subjects who stop pembrolizumab in a complete MRD response may be eligible for up to one year of additional pembrolizumab therapy if they experience MRD reappearance after stopping study treatment. This retreatment is termed the Second Course Phase of this study and is only available if the study remains open and the subject meets the following conditions:

- Stopped initial treatment with pembrolizumab after attaining an investigator-determined confirmed complete MRD response according to consensus criteria, and

9458- Protocol Version Date 28 Feb 2019

- Was treated for at least 24 weeks with pembrolizumab before discontinuing therapy
- Received at least two treatments with pembrolizumab beyond the date when the initial complete MRD response was declared
- Experienced an investigator-determined confirmed MRD reappearance after stopping their initial treatment with pembrolizumab
- Did not receive any anti-cancer treatment since the last dose of pembrolizumab
- Has a performance status of 0 or 1 on the ECOG Performance Scale
- Demonstrates adequate organ function as detailed in Section 5.1.2
- Female subject of childbearing potential should have a negative serum or urine pregnancy test within 3 days prior to receiving retreatment with study medication.
- Female subject of childbearing potential should be willing to use 2 methods of birth control or be surgically sterile, or abstain from heterosexual activity for the course of the study through 120 days after the last dose of study medication (Reference Section 5.7.2). Subjects of child bearing potential are those who have not been surgically sterilized or have been free from menses for > 1 year.
- Male subject should agree to use a condom starting with the first dose of study therapy through 120 days after the last dose of study therapy.
- Does not have a history or current evidence of any condition, therapy, or laboratory abnormality that might interfere with the subject's participation for the full duration of the trial or is not in the best interest of the subject to participate, in the opinion of the treating investigator.

Subjects who restart treatment will be retreated at the same dose and dose interval as when they last received pembrolizumab. Treatment will be administered for up to one additional year.

Visit requirements are outlined in Section 6.1 – Trial Flow Chart.

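### The Second Course trigger is disease progression in some sections and MRD reappearance in another, and progressing subjects are routed to two different phases

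*Combined protocol and SAP*

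**What the plan says.** Three sections open retreatment at progression. Section 5.8.1 covers subjects who stopped in a confirmed complete MRD response: "Subjects who then experience disease progression may be eligible for up to one year of additional treatment". The note to the 24-month item in Section 5.8 says that subjects stopping then "may be eligible for up to one year of additional study treatment if they progress after stopping study treatment", subject to Section 7.1.5.5. Section 7.1.5.3.2 moves subjects who are eligible under Section 7.1.5.5 from follow-up to the Second Course Phase when their disease progresses.

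Section 7.1.5.4, headed Second Course Phase, offers "additional pembrolizumab therapy if they experience MRD reappearance after stopping study treatment" and makes retreatment available only if every listed condition is met. Two of these conditions are "Stopped initial treatment with pembrolizumab after attaining an investigator-determined confirmed complete MRD response according to consensus criteria" and "Experienced an investigator-determined confirmed MRD reappearance after stopping their initial treatment with pembrolizumab".

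On where progressing subjects go, Section 7.1.5.3.3 says: "Once a subject experiences confirmed disease progression or starts a new anti-cancer therapy, the subject moves into the survival follow-up phase". The end of Section 5.8 likewise has each subject followed for overall survival after documented progression. Section 7.1.2.6 stops treatment and removes the subject from the study if morphologic relapse is found at any time.

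On prior status, Section 7.1.4.1 says "Subjects who a) attain a CR or b) complete 24 months of treatment with pembrolizumab may discontinue treatment", with an option to restart under Section 7.1.5.5. It places the Follow-Up Period in Section 7.1.5.4. Section 5.5.2 refers to retreatment for relapse after complete response and does not say which kind of relapse is meant.

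**The concern.** Section 12.3 treats MRD reappearance (conversion from MRD-negative to quantifiably positive) and morphologic relapse/progression (blasts in blood, or at least 5% in marrow) as different states. A rule that opens retreatment at one does not say the same as a rule that opens it at the other.

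Two things are at stake. The first is exposure: whether a subject in frank relapse may restart study drug for up to a year or must leave the study. The second is the outcome summaries. Section 3.2 relates MRD response to morphologic relapse-free and overall survival, and the footnote to Section 2.2 plans to describe duration of complete MRD response. Section 9.2 gives no event or censoring rule for a retreated subject. A subject whom one section places in a second course and another places in survival follow-up, where contact is only about survival status, could therefore be summarised in different ways.

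**Working it through.** No figure in the plan turns on this point, so the check sets the sections side by side.

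**Trigger and destination**

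| Section | Event | Consequence |
|---|---|---|
| 5.8 (note) | progression after stopping at 24 months | retreatment, if 7.1.5.5 is met |
| 5.8.1 | disease progression after stopping in complete MRD response | Second Course |
| 7.1.5.3.2 | disease progression in an eligible subject | Second Course |
| 7.1.5.4 | confirmed MRD reappearance | Second Course, only if all conditions are met |
| 5.8 (end) | documented disease progression | survival follow-up |
| 7.1.5.3.3 | confirmed disease progression | survival follow-up |
| 7.1.2.6 | morphologic relapse at any time | treatment stops, subject leaves the study |

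**Can one reading reconcile them?**

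1. *Progression means morphologic progression throughout.* Sections 5.8.1 and 7.1.5.3.2 then open retreatment at an event that is not the trigger in 7.1.5.4, and that 7.1.2.6 and 7.1.5.3.3 treat as the end of study treatment.
2. *Progression includes MRD reappearance throughout.* The triggers then overlap, but 7.1.5.3.3 sends a subject with MRD reappearance to survival follow-up, and 7.1.5.4 offers that same subject retreatment.
3. *Progression means MRD reappearance in 5.8.1 and 7.1.5.3.2, and morphologic progression in 7.1.5.3.3.* This is consistent, but it gives one term two meanings in adjacent subsections, and nothing in the text tells the reader to do so.

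No single meaning of the word makes the sections agree.

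**Prior response.** Sections 5.8.1 and 7.1.5.4 both require a confirmed complete MRD response, at least 24 weeks of treatment and at least two doses after the response was declared. Section 7.1.4.1 instead speaks of attaining a CR, with 24 months as an alternative. Under Section 2.1 every subject is already in morphologic complete remission at entry, so attaining a CR, read that way, identifies no response on study.

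**Cross-references.** Sections 5.8, 5.8.1, 7.1.4.1 and 7.1.5.3.2 all defer to Section 7.1.5.5. The numbering under 7.1.5 ends at 7.1.5.4. The pointer in 7.1.4.1 to the Follow-Up Period therefore lands on the Second Course Phase; follow-up visits are in 7.1.5.3.2.

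**Size.** Expected responders are 21 × 0.20 = 4.2 at the design alternative in Section 9.2, and 21 × 0.50 = 10.5 at the hypothesis in Section 3.1. These count responders. Retreatment also needs the 24 weeks, the two further doses, stopping in response, a later return of disease, no intervening anti-cancer treatment and an open study. The documents give no rates for these steps.

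**Primary analysis.** The stated operating characteristics are reproduced by exact binomial sums (stop at 0 of 12; success at 3 or more of 21):

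- Type I error: 0.0804 (stated .08).
- Power: 0.803 (stated 80%).
- Probability of 0 of 12 at a 20% rate: 0.80^12 = 0.069 (stated 0.07).
- Expected sample size at 5%: 0.95^12 = 0.5404, and 12 + (1 − 0.5404) × 9 = 16.1 (stated 16.1).

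None of these uses the retreatment rules. Under 5.8.1 and 7.1.5.4 a retreated subject has already been counted as a responder.

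**The case against.** The best defence is that Section 7.1.5.4 controls. It is the only list of entry conditions, and its wording is exclusive. The missing 7.1.5.5 looks like a numbering slip by one: 7.1.4.1 puts follow-up in 7.1.5.4 and the restart criteria in 7.1.5.5, and only the present 7.1.5.4 fits the second description. Section 12.3 defines progression only with the qualifier morphologic, so the unqualified phrase may be loose drafting. Section 7.1.5.3.2 also lists the start of retreatment as one way in which disease-status follow-up ends, so a branch exists.

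Much of this stands. It disposes of one inference a reader might draw from 7.1.4.1 and the 5.8 note: that a subject who completes 24 months without ever responding may be retreated. Both places make the option conditional on the cited section. If that is the present 7.1.5.4, a confirmed complete MRD response is required on every route. Section 5.8.1 requires it too.

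The defence does not remove the conflict. With 7.1.5.4 controlling, 5.8.1 and 7.1.5.3.2 still name another trigger, 7.1.5.3.3 still has no exception for retreatment, and 7.1.4.1 still lists 24 months as an alternative to CR. Eligibility for further study drug should not depend on guessing the intended section number.

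**Conclusion.** The trigger and the routing contradict each other as written, and the sections must be reconciled. This review does not judge which clinical rule is right. The possible consequence is up to one further year of study drug for a subject whom other sections remove from treatment.

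Three stronger conclusions are not supported:

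- The protocol does not clearly authorise retreatment in frank relapse. Sections 7.1.2.6 and 7.1.5.4 weigh against that reading; the fault is that 5.8.1 and 7.1.5.3.2 leave it open.
- The 4.2 above is not the expected number retreated. It is expected responders under one assumed rate. The number affected is not stated, and should be at most the few who respond and then meet the remaining conditions.
- It does not follow that MRD reappearance should be an event in every survival summary. That would change the morphologic relapse-free survival named in Section 3.2 and has no place in overall survival.

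The Simon decision rule is unaffected, on the assumption that retreated subjects have already had a complete MRD response. Section 9.2 makes secondary reporting mainly descriptive, which limits the statistical weight of the point.

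**What to change.** Reconcile Sections 5.5.2, 5.8, 5.8.1, 7.1.2.6, 7.1.4.1, 7.1.5.3.2, 7.1.5.3.3 and 7.1.5.4 to one trigger, one prior-response condition and one follow-up path. Use the terms defined in Section 12.3 in place of CR and unqualified disease progression. Whatever rule the investigators choose, state in 7.1.5.3.3, at the end of 5.8 and in 7.1.2.6 whether retreatment is an exception. Replace the references to 7.1.5.5, and correct the pointer in 7.1.4.1 to the Follow-Up Period.

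In Section 9.2, state that each outcome keeps its own event whether or not retreatment follows:

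- Duration of complete MRD response: MRD reappearance or relapse.
- Relapse-free survival: morphologic relapse or death.
- Overall survival: death.

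The cost is protocol wording. Sample size, visit schedule and decision rule do not change.

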### **5.9 Subject Replacement Strategy**

Subjects will be replaced only in the rare event that they are not evaluable, which will be defined as alive > 3 weeks after initiation of study treatment but without sufficient response data from bone marrow examination (refused response assessments, technical limitations precluding ability to review bone marrow status, etc.).

### **5.10 Clinical Criteria for Early Trial Termination**

Early trial termination will be the result of the criteria specified below:

1. Quality or quantity of data recording is inaccurate or incomplete
2. Poor adherence to protocol and regulatory requirements
3. Incidence or severity of adverse drug reaction in this or other studies indicates a potential health hazard to subjects
4. Plans to modify or discontinue the development of the study drug

In the event of Merck decision to no longer supply study drug, ample notification will be provided so that appropriate adjustments to subject treatment can be made.

9458- Protocol Version Date 28 Feb 2019

## 6.0 TRIAL FLOW CHART

### 6.1 Study Flow Chart

Trial Period:	Screening Phase	Treatment Cycles a								End of Treatment	Post-Treatment	
		1	2	3	4	To be repeated beyond 8 cycles					Discontinuation	Survival Follow-Up
Treatment Cycle/Title:	Screening Visit(s)					5	6	7	8			
Scheduling Window (Days):	-28 to -1		± 3	± 3	± 3	± 3	± 3	± 3	± 3	± 3	≤ 7 days post discontinuation	Every ~ 3 months
Administrative Procedures												
Informed Consent	X											
Inclusion/Exclusion Criteria	X											
Demographics and Medical History	X											
Prior and Concomitant Medication Review	X	X	X	X	X	X	X	X	X	X	X	
Pembrolizumab Administration		X	X	X	X	X	X	X	X	X		
Post-study anticancer therapy status												X
Survival Status												X
Clinical Procedures/Assessments												
Review Adverse Events	X	X d	X	X	X	X	X	X	X	X	X	
Full Physical Examination	X										X	
Directed Physical Examination		X d	X	X	X	X	X	X	X	X		
Vital Signs and Weight	X	X d	X	X	X	X	X	X	X	X	X	
ECOG Performance Status	X	X d	X	X	X	X	X	X	X	X	X	
Laboratory Procedures/Assessments: analysis performed by LOCAL laboratory												
Pregnancy Test – Urine or Serum β-HCG	X b											
PT/INR and aPTT	X b											
CBC with Differential	X b	X d	X	X	X	X	X	X	X	X	X	

9458- Protocol Version Date 28 Feb 2019

Trial Period:	Screening Phase	Treatment Cycles a								End of Treatment	Post-Treatment	
Treatment Cycle/Title:	Screening Visit(s)	1	2	3	4	To be repeated beyond 8 cycles				Discontinuation		Survival Follow-Up
						5	6	7	8			
Scheduling Window (Days):	-28 to -1		± 3	± 3	± 3	± 3	± 3	± 3	± 3	≤ 7 days post discontinuation		Every ~ 3 months
Comprehensive Serum Chemistry Panel	X b	X d	X	X	X	X	X	X	X	X		
Urinalysis	X b									X		
T3, FT4 and TSH	X b									X		
Efficacy Measurements												
Bone Marrow Examination	X	X e	X e		X e			X e,f		X e,f	X e	
Tumor Imaging	X c									X c		
Tumor Biopsies/Archival Tissue Collection/Correlative Studies Blood												
Archival or Newly Obtained Tissue Collection	X g	X g	X g		X g					X g		
Correlative Studies Blood Collection	X g		X g		X g					X g		

a Treatment cycles will occur every 21 ± 3 days
 
b Screening laboratory assessments should be performed within 10 days prior to the first dose of pembrolizumab, while urine/serum pregnancy test must be performed within 3 days of the first dose of pembrolizumab.
 
c Tumor imaging is only required in patients suspected of having sites of extramedullary disease.
 
d In the event that adequate clinical and laboratory assessments performed for screening purposes occur within 3 days of the start of Cycle 1, they do not need to be repeated for Cycle 1.
 
e Bone marrow examinations should be performed 3 ± 1 days prior to the start of the subsequent cycle (i.e., Day 18-20) to provide adequate time for interpretation. At a minimum, bone marrow exams will include an evaluation of morphology as well as a repeat analysis of whatever study (or studies) detected MRD at the time of enrollment; other studies may be included as clinically indicated. An end-of-treatment bone marrow examination does not need to be repeated if morphologic relapse/progression is identified on a scheduled surveillance examination.
 
f For those eligible to continue beyond Cycle 8, the timing of subsequent bone marrow exams will be left to the treating investigator, though no less often than every 3 months while receiving study treatment will be recommended.
 
g Details regarding planned correlative analyses on bone marrow and blood are described in Section 7.1.2.7.
												

9458- Protocol Version Date 28 Feb 2019

